### 3-Month and 6-Month Post-Intervention Follow-Up

Survey measures and assessments of glycemic control will be repeated 3 months and 6 months after the final SMA.

## **6.4 Description of Study Procedures/Evaluations**

### **Study Visits**

All SMA appointments will be scheduled at the time that consent is obtained. Biometric data (height, weight, BMI, A1c) will be obtained as part of routine care. Data from 14 days prior to the visit for the CGM will be obtained through online software used to securely query these devices for routine clinical care (Dexcom Clarity). Secure REDCap surveys will be sent to participants via email 1 week before their visit (including the T1DAL, DSMP, SEDS, PAID, CGM Benefits and Burdens, and an SMA evaluation for patients; and for parents: P-T1DAL, P-DSMP, P-SEDS, and P-PAID, CGM Benefits and Burdens, and SMA evaluation). If the surveys have not been completed at the time of the visit participants will be given the option to complete the measures using an iPad or paper surveys in clinic at the time of their visit.

Prior to the study visit, chart review will be conducted to assess the interval incidence of DKA, severe hypoglycemia, ED visits, and hospital admissions. This will be conducted in accordance with the HIPAA rules. Information obtained through chart review will be

corroborated with patients during study visits to ensure accuracy. Biometric data, CGM data obtained from Clarity, and A1c values will be provided to participants as part of routine clinical care. The results from the battery of questionnaires will not be provided to patients.

### **Primary Outcome**

Given the novelty of the SMA approach for underserved youth and promotion of CGM technology uptake and sustained use, feasibility and acceptability of the intervention will serve as the primary outcome measure. We will track recruitment, enrollment, participation, and retention through a CONSORT table (Table 2) for the intervention group. Feasibility benchmarks include: recruitment (>60% of reached/eligible participants), CGM initiation, (>80%), SMA sessions attended (>80%), and retention (>80%). In addition, feasibility encompasses demographic characteristics of the enrolled sample, with enrollment and overall increased uptake of CGM among youth from historically underrepresented racial and ethnic backgrounds (Black race and/or Latinx ethnicity) and income levels. Attrition data and team feedback will help determine how recruitment rates may be improved. Acceptability will be assessed using satisfaction surveys and determined by a high level of satisfaction with participation, perceived utility of the intervention content, and perceived benefit from participation (>80% reporting that they were satisfied and perceived utility and benefit as indicated by a Likert scale score of 4 or 5). We will report summary statistics on each feasibility and acceptability item in the questionnaires (mean and standard deviation well as percent answering a specific Likert level). Acceptability also will be examined by key demographic characteristics, including participant age and race/ethnicity.

Parent-child dyads will participate in semi-structured interviews to assess satisfaction with the SMA. Thematic analysis of qualitative data will be conducted by two team members who will independently review interview transcripts to generate initial codes. Initial codes will be discussed by the group to generate a list of second-cycle codes and each team member will then apply the coding framework to all transcripts before identifying dominant themes. ATLAS.ti software will be used to organize and analyze the qualitative data.

### **Secondary Outcomes**

Secondary outcomes will include CGM metrics that can be used to assess effects on glycemic control and survey measures designed to explore potential psychosocial benefits, including changes in self-management skills, self-efficacy, treatment satisfaction, and diabetes related quality of life. CGM time in range from 70-180 mg/dL (TIR) has been correlated with A1c values, which have classically been used as primary outcomes in T1D studies because of their association with microvascular complications. We have chosen to focus on use TIR rather than A1c because of the propensity for A1c variation in Non-Hispanic Black youth who also have a higher propensity for hemoglobin variants. CGM data will be obtained at each follow up visit through online software used to securely query the device for routine clinical care. Glycemic variability indicators will be obtained from CGM downloads for the 14 days prior to a follow-up data collection time point. As guided by published standardized

CGM metrics, data will be transformed to identify number of measurements and percent TIR, time below range (<70 mg/dL) (TBR), and time above range ( $\geq 180$  mg/dL) (TAR), mean sensor glucose, and coefficient of variation (CV) of glucose values during each 14-day period. We also will track the percent CGM wear time.

CGM data will be analyzed using library GLU in R.73 using mixed effect models. These models will quantify the impact of our intervention on glucose control over time. The independent variables will be baseline time in range, child age, and a random subject effect to account for correlation of measurements on the same subject. Interaction terms of age and baseline time in range with the intervention will explore possible effect modification ( $p < 0.10$ ) of these characteristics. We will also explore differences between intervention time points and average outcome by parent education level and income.

A battery of validated survey measures exploring diabetes-specific self-management skills and quality of life will be completed by the child and caretaker, including: Type 1 Diabetes and Life (T1DAL), Diabetes Self-Management Profile (DSMP), Self-Efficacy for Diabetes (SEDS), and Problem Areas in Diabetes (C-PAID). Perceived benefits and barriers to CGM use will be assessed using the CGM Benefits and Burdens scale. Surveys will be completed by a single, consistent parent/caregiver throughout the study, preferably the one most involved in medical care.

We will summarize self-management skills and treatment satisfaction from baseline to completion of the SMA visits, as well as 3-months and 6-months after completion of the SMA intervention. Differences in participant self-management skills and patient satisfaction will be reported as mean Likert scale score and standard deviation. Similar analysis using linear longitudinal regression analysis will be conducted. Results will be reported as least-squares means (LSMEANS) with standard errors. Casewise deletion will be used to handle missing data.

### **6.5 Study Team Training and Intervention Reliability**

All personnel involved in the conduct of this study have completed Human Subjects Protection and ICH GCP training. Study team members will be trained in how to properly score the various questionnaire results, so that scoring practices are objective and standardized. Data collection is the responsibility of the clinical trial staff at the site under the supervision of the site investigator. The investigator is responsible for ensuring the accuracy, completeness, legibility, and timeliness of the data reported. Separate semi-structured qualitative interviews will be conducted with patients and parents upon completion of the study to gain insight into satisfaction with the SMA visits. The sessions will be recorded on two separate devices and subsequently transcribed to allow for data analysis.

### **6.6 Concomitant Interventions and Procedures**

Not applicable

## **Section 7: Safety Assessments and Reporting**

### **7.1 Adverse Events (AEs)**

Risk to participants is minimal. While it is unlikely that participants will experience any risk, there may be minimal distress associated with completing questionnaires that ask about diabetes management, mood, or diabetes technology burden. Participants may also feel some distress related to discussing diabetes management, mood, or technology burden in the group SMA setting. Another potential source of risk in this study is the risk of gathering sensitive social, behavioral, and medical information. Data collection via the internet will be conducted through secure applications (REDCap) and no more than minimal risk.

### **7.2 Study Halting Rules**

This study may be temporarily suspended or prematurely terminated if there is sufficient reasonable cause. Written notification, documenting the reason for study suspension or termination, will be provided by the suspending or terminating party to study participants, investigator, funding agency, the sponsor and regulatory authorities. If the study is prematurely terminated or suspended, the Principal Investigator (PI) will promptly inform study participants, the Institutional Review Board (IRB), and sponsor and will provide the reason(s) for the termination or suspension. Study participants will be contacted, as applicable, and be informed of changes to study visit schedule.

Circumstances that may warrant termination or suspension include, but are not limited to:

- Determination of unexpected, significant, or unacceptable risk to participants
- Demonstration of efficacy that would warrant stopping
- Insufficient compliance to protocol requirements
- Data that are not sufficiently complete and/or evaluable
- Determination that the primary endpoint has been met
- Determination of futility

Study may resume once concerns about safety, protocol compliance, and data quality are addressed, and satisfy the sponsor, IRB and/or Food and Drug Administration (FDA).

## **Section 8: Statistical Considerations and Analysis**

### **8.1 Statistical and Analytical Plans (SAP)**

There will not be a formal SAP

### **8.2 Statistical Hypotheses**

Primary Outcome: feasibility and acceptability of SMA among underserved youth with T1D.

Hypothesis 1a. Rates of SMA retention (>80%) at 12-months and satisfaction with visits (>80%) will be high.

Null Hypothesis 1a: n/a

Hypothesis 1b: Thematic analysis of semi-structured interviews will identify high satisfaction with SMA.

Null Hypothesis 1b: n/a

Secondary Outcome: preliminary impact of SMA on glycemic control, self-management skills, self-efficacy, diabetes related quality of life, and treatment satisfaction among underserved children with T1D and their caregivers

Hypothesis 2a: CGM percentage wear time and sustained use, as defined by use within the 2 weeks prior to the visit, will be greater upon completion of the SMA intervention at 12 months compared to baseline

Null Hypothesis 2a: CGM percentage wear time and sustained use, as defined by use within the 2 weeks prior to the visit, will not be significantly different upon completion of the SMA intervention at 12 months

Hypothesis 2b: CGM time in range (70-180 mg/dL) will be greater and the glucose management indicator (GMI) lower for youth upon completion of the SMA intervention group at 12 months compared to baseline.

Null Hypothesis 2b: CGM time in range (70-180 mg/dL) will not be significantly different upon completion of the SMA intervention at 12 months

Hypothesis 2c: Diabetes-specific quality of life, self-management behaviors, and self-efficacy scores will be greater upon completion of the SMA intervention at 12 months compared to baseline.

Null Hypothesis 2c: Diabetes-specific quality of life, self-management behaviors, and self-efficacy scores will not be significantly different upon completion of the SMA intervention at 12 month

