## Study Design Schematic

**Table 1.** Schedule of study procedures.

Construct	Measure	Initial SMA	3mo SMA	6mo SMA	9mo SMA	12mo SMA	15mo	18mo
14-Day CGM Markers of Glycemic Control	Mean CGM Glucose	X	X	X	X	X	X	X
	Coefficient of Variation	X	X	X	X	X	X	X
	Glycemic Mgmt Indicator (GMI)	X	X	X	X	X	X	X
	CGM Wear Time	X	X	X	X	X	X	X
	CGM TIR	X	X	X	X	X	X	X
	CGM TBR	X	X	X	X	X	X	X
	CGM TAR	X	X	X	X	X	X	X
A1c		X	X	X	X	X	X	X
Youth Surveys	T1DAL	X	X	X	X	X	X	X
	DSMP	X	X	X	X	X	X	X
	SEDS	X	X	X	X	X	X	X
	PAID	X	X	X	X	X	X	X
	CGM Ben & Bur	X	X	X	X	X	X	X
	SMA Evaluation	X	X	X	X	X	X	X
Parent Surveys	P-T1DAL	X	X	X	X	X	X	X
	P-DSMP	X	X	X	X	X	X	X
	P-SEDS	X	X	X	X	X	X	X
	P-PAID	X	X	X	X	X	X	X
	CGM Ben & Bur	X	X	X	X	X	X	X
	SMA Evaluation	X	X	X	X	X	X	X
Semi-Structured Dyad Interview						X		

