### **3.4 Secondary Outcome Measure(s)**

Secondary outcomes will include CGM metrics and chart review that can be used to assess effects on glycemic control, and survey measures designed to explore potential psychosocial benefits, including changes in self-management skills, self-efficacy, treatment satisfaction, and diabetes related quality of life. We will look at differences in the following measures from baseline to completion of the SMA intervention, as well as 3 and 6-months after completion of the SMA intervention: 1) CGM time in range from 70-180 mg/dL (TIR), 2) time below range (< 70 mg/dL) (TBR), 3) time above range ( $\geq$  180 mg/dL) (TAR), 4) mean sensor glucose, 5) coefficient of variation (CV) of glucose, 6) CGM wear time, 7) episodes of DKA, 8) episodes of severe hypoglycemia, 9) ED visits, hospital admissions, 10) A1c, 11) qualitative measures exploring self-management, satisfaction, health related quality of life as measured with the following validated questionnaires (T1DAL, DSMP, SEDS, C-PAID, CGM Benefits and Burdens scale).

CGM time in range from 70-180 mg/dL (TIR) has been correlated with A1c values, which have classically been used as primary outcomes in T1D studies because of their association with microvascular complications. This connection to long-term complications also makes TIR a better primary outcome measure than survey measures because this data has greater potential to alter real-world prescribing practices than patient perceptions captured by questionnaire. We have chosen to focus on TIR rather than A1c because of the propensity for A1c variation in Non-Hispanic Black youth who also have a higher propensity for hemoglobin variants.

Additional CGM derived measures of glycemic control are commonly used outcomes in studies of T1D technology. A1c has been included because it has classically been considered the gold standard. The acute complications of T1D being examined are also frequently used in T1D studies. The survey measures exploring quality of life are among the most widely accepted outcome measures in their specific topic areas.

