## **Section 4: Study Design**

Dyads of youth with T1D aged 8-12 years and their primary diabetes caretakers identifying as non-Hispanic Black or Latinx will be recruited to participate in a prospective cohort pilot study exploring feasibility and acceptability of SMA and the impact on glycemic control, self-management skills, and health related quality of life. This trial will employ an enrollment visit, SMA visits every 3 months over a 12-month study period, and a follow-up 6-month observational period to continue to evaluate outcomes once patients return to routine individual follow up care. The study will include a single intervention group participating in the SMA visits (n=20).

All staff participating in the SMA visit will receive comprehensive training on how to facilitate the SMA discussion sessions effectively. All topics that will be covered at each SMA visit will be reviewed by the study staff ahead of the visit. Potential participants will

be screened for participation using our electronic medical records system and will be approached during routine clinical visits. After explaining all study procedures, informed consent using an IRB-approved consent form will be obtained for all participants. After obtaining consent, a blinded Dexcom G6 CGM will be placed on the participant. Participants will be instructed to wear the blinded CGM for 10 days in order to obtain baseline glycemic control data prior to starting the SMA visit intervention. At the completion of the 10 day wear period, participants will mail back the blinded CGM in a pre-addressed envelope so that the data can be assessed within 30 days of the wear time. Because SMA visits will be used in place of routine clinic visits and because participants will not require any additional in person study visits, we anticipate significant interest in participation with minimal barriers. Secure REDCap surveys will be sent to participants via email 1 week before each follow-up visit. If the surveys have not been completed at the time of the visit the participant will be asked to complete the measures using an iPad or paper in clinic at the time of their visit. Youth who elected not to use a CGM for routine clinical care, will be asked to wear a blinded professional CGM for 10 days prior to each visit whenever possible.

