**Follow Up SMA:** Follow up SMA will be scheduled 3, 6, 9, and 12 months from the initial group visit. CGM data from 14 days prior to each SMA will be reviewed by the endocrinologist ahead of the group visit. Discussions and education guided by the facilitators will focus on issues that have been described in the literature as potential barriers to CGM use and adherence. Recurrent alerts and alarms can result in alarm fatigue, and falsely low glucose readings and sensor or transmitter failures have been cited as reasons for discontinuing CGM use. The continuous nature of CGM data has been shown to place significant demands on patients and their families, and to create stress related to the constant need for diabetes-related attention. Follow up visits will focus on optimized use of CGM alarms and prevention of alarm fatigue. Psychologists and CDCES will discuss strategies to cope with the on-body presence and potential embarrassment resulting from CGM wear and to optimize parent-child communication surrounding CGM. Nutritionists will highlight the impact of different foods on glycemic trends and discuss strategies to optimize control. SMA will also allow ample opportunity to jointly review de-identified CGM reports and how to effectively interpret data and make management changes in response to CGM data, empowering patients and families to improve self-management and reduce stress related to CGM use. Active participation in discussions and group exercises will continue to strengthen the community feeling and social support network within the SMA group. Any participant that chooses to discontinue CGM during the 12 month study period will wear a blinded CGM 10 days prior to the follow up visits to allow for complete data collection. Upon completion of the final SMA visit at month 12, dyads will be contacted to schedule a semi-structured interview and will then return to standard clinical care.

**3-Month and 6-Month Post-Intervention Follow-Ups:** Survey measures and assessments of glycemic control will be repeated after 3 months and 6 months of routine clinical care to assess for long-lasting effects of the intervention.

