## **5.2 Inclusion Criteria**

In order to be eligible to participate in this study, an individual must meet all of the following criteria:

1. Patients clinically diagnosed with T1D managed with insulin injections for at least 1 year
2. Non-Hispanic Black or Latinx ethnicity
3. Public healthcare insurance
4. Male or female ages  $\geq 8$  and  $\leq 12$  years
5. No prior use of CGM within 60 days of enrolment
6. Poorly controlled T1D: one A1c value  $> 8\%$  in the preceding year
7. Fluent in English as the Dexcom technology is currently available only in English
8. Participation of the primary diabetes caregiver

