## **6.3 Study Interventions and Follow-Up**

### Enrollment visit

Those who have met eligibility criteria and express interest in study participation will meet with study staff to review the study specifics in more detail and obtain consent. Randomization will occur after consent has been obtained. A blinded Dexcom G6 pro

CGM will be placed on the patient and be worn for 10 days in order to collect baseline data prior to starting the SMA intervention. Phone applications that will allow for sharing of CGM data between patients and the diabetes clinical care team will be downloaded and established before the end of the visit.

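### Hypothesis 2a and the wear-time outcome compare 12-month CGM use and wear with a baseline that carries no information on uptake, and no text keeps blinded-sensor wear out of percent wear time

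*Combined protocol and SAP*

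**What the plan says.** Section 8.2 frames Hypothesis 2a as follows: "CGM percentage wear time and sustained use, as defined by use within the 2 weeks prior to the visit, will be greater upon completion". The contrast is month 12 against baseline, and no sensor type is named. Section 3.4 lists CGM wear time among the secondary outcomes and plans the same contrast: "We will look at differences in the following measures from baseline to completion of the SMA intervention".

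Four other parts of the protocol determine what baseline and 12-month values can be.

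- **Eligibility.** Section 5.2, criterion 5: "No prior use of CGM within 60 days of enrolment".
- **Baseline sensor.** Section 4: "Participants will be instructed to wear the blinded CGM for 10 days in order to obtain baseline glycemic control data". The enrollment visit in 6.3 says the same of the blinded sensor, which is to "be worn for 10 days in order to collect baseline data prior to starting the SMA intervention". No other sensor is described before the initial SMA. Table 1 nevertheless schedules CGM wear time at the initial SMA, in the block headed "14-Day CGM Markers of Glycemic Control".
- **Follow-up sensor for non-users.** Section 4: "Youth who elected not to use a CGM for routine clinical care, will be asked to wear a blinded professional CGM for 10 days" before each visit, as far as possible. A participant who stops CGM "will wear a blinded CGM 10 days prior to the follow up visits to allow for complete data collection"; 6.3 repeats this.
- **Analysis.** Section 8.4 gives wear time one sentence, saying that it will be tracked. It states no sensor type, denominator or rule for blinded wear. Section 8.1 says there will be no formal SAP.

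Table 2 (section 3.3) separately lists the percentages of children who start and who continue CGM, at all assessment points. Initiation above 80% is a primary feasibility benchmark. Continuation is not defined and has no benchmark.

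**The concern.** Section 2.2 gives uptake and sustained use of CGM as a purpose of the SMA, and 2a is the only hypothesis in 8.2 that addresses it. A change from baseline is informative only if the baseline measures the same thing as the follow-up and could have differed. Here it does not.

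If the child's own CGM is what counts, baseline is essentially zero by eligibility. The change can then only be upward and equals the 12-month level, so testing it adds almost nothing. If blinded wear counts, baseline reflects compliance with a study request, and the same request before follow-up visits can hold up the 12-month figure among children who have abandoned CGM. A later trial that takes its adherence assumption from this pilot (section 2.4 expects the results to inform randomized studies) could inherit a wear figure that is partly study-imposed.

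**Working it through.** The plan gives no alpha, test, power or expected effect for 2a, so there is no stated figure to reproduce. Inputs from the documents: up to 20 dyads (8.5), two-tailed p-values (8.4), 10 days of blinded wear (Section 4, 6.3), and a 14-day CGM window before each visit (Table 1, 6.3, 8.4). Assumed for illustration: all 20 children analysed, a sign test, the alpha levels, and the continuation, wear and compliance rates below.

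**Personal CGM only.** With baseline zero for everyone, k users at 12 months means k increases and no decreases. Exact two-sided p = 2 × 0.5^k.

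- k = 5: 2 × 0.5^5 = 0.0625
- k = 6: 2 × 0.5^6 = 0.031
- k = 8: 2 × 0.5^8 = 0.0078

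Rejection therefore needs 5 of 20 users at alpha 0.10, 6 at 0.05 and 8 at 0.01. Six of 20 is 30% (exact 95% CI 11.9% to 54.3%), so the null falls at 0.05 with 14 of 20 children, 70%, not using CGM. If true use were 40%, the chance of at least 6 users would be 0.87.

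**Blinded wear counted.** Full blinded wear fills 10/14 = 71.4% of the window. At baseline this needs all 10 days to fall within the 14 days before the initial SMA. The gap between enrolment and that visit is not stated, so the window may hold all, part or none of the wear.

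Let f be the share continuing personal CGM and w their percent wear. Then reported wear = f × w + (1 − f) × 71.4; personal wear = f × w; change from a 71.4% baseline = f × (w − 71.4). With w = 90 and full blinded compliance:

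| Share continuing | Reported wear | Personal wear | Change from baseline (points) |
|---|---|---|---|
| 0% | 71.4% | 0% | 0 |
| 25% | 76.1% | 22.5% | +4.6 |
| 50% | 80.7% | 45.0% | +9.3 |
| 80% | 86.3% | 72.0% | +14.9 |

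With w = 70 and half continuing, reported wear is 70.7% and the change is −0.7. If non-users wear only half the blinded days at follow-up (5/14 = 35.7%), reported wear is 35.7% with none continuing and 0.5 × 90 + 0.5 × 35.7 = 62.9% with half continuing.

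**Effect of the missing definition.** Take half the children continuing at 90% wear. The change from baseline in points is:

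- personal wear at both times: 45.0 − 0 = +45.0
- blinded wear counted at 12 months only: 80.7 − 0 = +80.7
- blinded wear counted at both times: 80.7 − 71.4 = +9.3
- blinded wear counted at baseline only: 45.0 − 71.4 = −26.4

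The same children give a rise or a fall depending on a choice that the protocol does not make.

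**The case against.** Four points can be made in defence.

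First, the protocol's language separates use from blinded wear. Section 4 contrasts youth who choose not to use CGM in routine care with the blinded sensor they are asked to wear, and both Section 4 and 6.3 describe blinded wear after discontinuation as a means of completing the data. CGM data are also said to come from software that queries devices for routine care. A reader might infer that the plan counts blinded wear as CGM use; the wording points the other way. This stands for the word use. It does not settle percent wear time, which Table 1 places at the initial SMA when the only sensor described is the blinded one. For use, it leads straight to the zero baseline.

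Second, initiation is already a primary benchmark and continuation is tracked in Table 2, so a low continuation rate would appear beside a high wear figure. This stands, and it limits the point. But continuation is undefined, and Table 2 does not alter the 2a comparison.

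Third, a test that rejects at 6 of 20 is weak rather than wrong: use really would have risen from zero, and least-squares means would be shown alongside. That is fair. The complaint is that the comparison is uninformative, not that it is false.

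Fourth, the 71.4% figure is an upper bound, because it needs every non-user to wear the blinded sensor in full and Section 4 asks for this only as far as possible. This also stands, and is why the half-compliance figures are given.

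**Conclusion.** The concern holds for Hypothesis 2a and for the wear-time difference in 3.4, and no further. Personal CGM use at entry is zero by eligibility, so the test against baseline is nearly trivial (6 of 20 users gives p = 0.031 under the assumed sign test and alpha). Blinded wear is not kept out of percent wear time at either end, so reported 12-month wear could be as high as 71.4% with no child using a personal CGM, or 35.7% at half compliance. These figures rest on the 14-day window and on the stated assumptions about test, compliance, continuation and wear.

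A reader might go on to infer that the trial has no sound measure of uptake, or that reported wear will be inflated. The documents support neither: Table 2 tracks initiation and continuation, and the size and even the presence of inflation depend on compliance and on how the downloads are handled. Nor is the blinded wear itself a fault, since it is a reasonable way to complete time-in-range data. This is a secondary hypothesis in an unpowered single-arm pilot; what is affected is the interpretation of 2a, not the sample size or the primary outcome.

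**What to change.** In 3.4, 8.2 and 8.4:

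1. Define use and percent wear time for 2a from the child's own unblinded CGM over the 14-day window. Score children who stopped or never started as 0.
2. Keep blinded-sensor data for the glycemic metrics, and report blinded wear separately as a measure of data completeness.
3. Replace the test against baseline with the proportion using their own CGM at 12 months, with an exact 95% CI, plus mean personal wear. Give the continuation item in Table 2 the same definition.
4. Use as denominator all children who enrolled, including any later replaced under 5.7 and 8.5, because the per-protocol set in 8.3 leaves out those who withdraw. Count withdrawn children with unknown use as non-users, and also show the figure among those with known status.

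The cost is wording in three sections and a blinded/unblinded flag on each download. No visits or participants are added. Reported use and wear may be lower than under a definition that lets blinded wear in.
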